## 7. Safety of MSC administration

In a 2016 publication Ankrum et al noted that nearly 350 clinical trials had been, or were being, conducted with MSC preparations; 190 of these used allogeneic cells. These authors concluded that “Importantly, allo-MSC therapy has consistently been shown to be safe...” In 2012 Lalu and associates published a meta-analysis of clinical trials examining the safety of systemic MSC administration. These authors concluded that: “Our analysis was unable to detect associations between MSC treatment and the development of acute infusional toxicity, organ system complications, infection, death, or malignancy. There was, however, a significant association between MSC administration and transient fever....aside from fever, the published current clinical trials suggest that the administration of MSCs is safe”. Importantly, hyperacute rejection-like symptoms have not

been reported in human patients who receive allogeneic MSC therapy

Of relevance, the MSCs being used in the present study are the same (CardioCell/Stemedica) as used in a study of patients with NICM. This was a Phase 2a study in which MSCs were administered intravenously to 23 patients, the results of which are outlined in the Background, Section 2. There were no clinically significant adverse effects observed.

### ***8. Safety issues surrounding development of immune responses to allogeneic MSCs with repeated injections.***

The safety of a single dose of MSCs has been compellingly demonstrated. Although the safety of multiple injections of MSCs has as yet to be *definitively* determined, multiple intravenous injections have frequently been given to patients with no, or minimal serious sequela. This experience is summarized in the following paragraphs.

#### ***Patients with graft vs. host disease (an immunocompromised cohort of patients).***

Chen et al reported a systematic review and meta-analysis of patients with steroid-refractory acute graft-vs-host disease (aGVHD) given multiple intravenous allogeneic MSC injections. A total of 301 patients from thirteen studies were included. Of these, 9 patients (3%) developed responses that were deemed either not likely, or possibly, related to the MSC infusion. Of particular note is the study by Kurtzberg et al. Seventy-five pediatric patients were studied. The mean total number of infusions received was  $9.7 \pm 3.97$ , with a median of 10.0 (range, 1 to 20), with 40 patients (53.3%) receiving >8 infusions. Only 1 patient (1.3%) experienced an infusion-related reaction (ie, rise in body temperature, increased breathing, and decreased oxygen saturation) after the third and fourth infusions, which resolved without sequela. The authors concluded that MSC infusion "...appears to have a benign safety profile". Infusions were well tolerated, with only 2 reported reactions occurring in the same patient out of more than 500 infusions administered during the course of the study. There were no cases of ectopic tissue formation. The number and type of events reported are consistent with a severely immunocompromised aGVHD patient population. At study entry, these patients had a complicated history and suffered from a variety of severe medical conditions. Treatment...did not lead to apparent additional toxicities and was well tolerated in this population. Furthermore, this therapy was not associated with hematologic or renal

toxicity."

***Patients with Chronic Obstruction Pulmonary Disease (an immunocompetent cohort of patients).***

Sixty-two patients with chronic obstruction pulmonary disease (COPD) were randomized to double-blinded IV infusions of either allogeneic MSCs or vehicle control. Patients received four monthly infusions ( $100 \times 10^6$  cells/infusion) and were subsequently followed for 2 years. The authors report that "There were no infusional toxicities and no deaths or serious adverse events (SAEs) deemed related to MSC administration. There were no significant differences in the overall number of adverse events, frequency of COPD exacerbations, or worsening of disease in patients treated with MSCs."

In our study, during MSC infusion, we will carefully observe our patients to determine whether clinically important safety-related immune response issues arise acutely.

We will also test for long-term development of immune cell reactivity, development of anti-HLA antibodies, and whether any positive test responses are associated with adverse clinical outcomes.

***9. Issue of development of immune responses to allogeneic MSCs interfering with potential beneficial effects of MSCs.***

Because it had been demonstrated that MSCs do not constitutively express Major Histocompatibility Class (MHC) II antigens or the B7 and CD40 ligand costimulatory molecules, and because MSCs have immunosuppressive and immunomodulatory properties, it became commonly accepted that MSCs are immunoprivileged and not eliminated by the immune surveillance system when administered to HLA mismatched recipients. However, studies also demonstrated that while MSCs do not constitutively express HLA class II molecules, the addition of IFNy for 48 hours induced greater than 90% of cells to express HLA class II. This finding constitutes one of a large number of studies demonstrating that MSCs are not immunoprivileged—rather, they do generate immune responses when administered to HLA mismatched recipients and are cleared more rapidly than syngeneic MSCs.

Despite this lack of persistence, it appears MSCs are relatively protected from immune detection. Thus, Ankrum and colleagues presented the results of a study in which the relative persistence of allo-fibroblasts vs. allo-MSCs

was compared. The study showed that fibroblasts died by day 10 and MSCs by day 20—in other words, although the MSCs were not immune privileged, they had some protection against immune rejection (the authors refer to this as *immune evasive*) resulting in longer persistence than the non-MSCs. This concept was also documented by Galipeau et al who used murine MSCs transfected with the gene expressing erythropoietin as a reporter for persistent MSC functionality. MSCs were injected subcutaneously in either MHC-mismatched allogeneic or matched syngeneic mice. Although expression of erythropoietin lasted for a longer time in the syngeneic mice, the mismatched MSCs still produced erythropoietin for over 30 days

It therefore has been unequivocally demonstrated that MSCs are not immune-privileged, as originally proposed. They eventually are eliminated from mismatched hosts through immune responses. However, MSCs do persist for a limited time (longer than other types of mismatched cells) and are, thus, immune evasive. The issue relating to potential efficacy therefore becomes whether MSCs persist long enough to exert a therapeutic effect. The literature supports a positive response to this question, as the concept has been advanced that the relevant activities of the MSCs need only a limited time to produce their effects. Such a mechanism has been referred to as a “hit-and-vanish” or “hit and run” mechanism.

The results of our own studies in mice with either AMI or ICM (reviewed in part; see Background, Section 3, and Figure 3.2 and 3.3) relate to this issue. AMI or ICM was created and the mice were treated by intravenous administration of *human* MSCs. This therefore was a *xenograft* model, susceptible to the immune surveillance issues discussed above. We found:

- Human MSCs, injected IV into mice with AMI, persist in a viable state in the heart for at least 7 days, and when injected into mice with ICM, persist in a viable state in the heart for at least 20 days.
- The number and duration of the persisting MSCs are sufficient to exert biologically important effects—IV administered MSCs led to a) significant immune modulatory effects (among these, and perhaps most important, a decrease in spleen and heart NK cells) and b) marked improvement in LV function in both AMI and in ICM models.

- Importantly, in the ICM model MSCs were injected at time 0 and a repeat dose was administered 3 weeks later. No acute adverse effects occurred following the second injection. Additionally, the double injection led to a marked beneficial effect in myocardial function as measured by echocardiography at weekly intervals, with a final measurement at 7 weeks (see Background, Section 2).

It therefore appears that a beneficial myocardial functional effect is not dependent on MSCs persisting indefinitely in the host—benefit appears to accrue from MSCs secreting anti-inflammatory and other factors early after their injection. Perhaps intravenous administration is a *desirable* strategy, as most of the MSCs injected intravenously embed in non-cardiac tissue (lungs, spleen, kidneys)—i.e., in tissues that are not the site of inflammation, a factor that avoids exposing the MSCs to activation factors, such as IFN $\gamma$ , that are present at high levels in inflamed tissues and that lead to the expression of HLA class II molecules, which would lead to more rapid immune-mediated removal of the cells.

This intravenous strategy, along with the potential efficacy of a “hit and vanish” mechanism, could effectively reduce the deleterious effects of persistent inflammation (as we postulate exists in LVAD patients) even without long-term persistence of a single MSC injection. Our trial is also important from the perspective of testing the efficacy and safety of multiple IV injections of MSCs, as it will be the first study undertaken in cardiac patients to test a multi-injection strategy.

And while safety of MSC administration has been compellingly demonstrated (at least over the short term), the long-term effects have not been extensively documented. It is perhaps encouraging to know that because MSCs do elicit immune responses that eliminate the cells over weeks or months, long term problems would not be anticipated.

#### **10. Central hypotheses for carrying out the proposed study:**

Compelling preclinical data indicate that chronic inflammation contributes to the progressive myocardial dysfunction occurring post-AMI and in HF. It has now also been definitively demonstrated in preclinical models that intravenously delivered MSCs to mice with either AMI or ICM improves myocardial function, an effect

caused at least in part by systemic MSC-induced anti-inflammatory effects. And a recently published phase 2a clinical study provides evidence suggesting that intravenous administration of MSCs to patients with NICM decreases circulating NK cells; importantly, the magnitude of the MSC-induced decrease in NK cells was significantly associated with the magnitude of improvement in LV function. Experimental data are also compatible with the conclusion that the beneficial anti-inflammatory effects are transient, and that multiple injections would likely be necessary to achieve persistent beneficial effects on myocardial function. Finally, LVAD patients have persistent, and strikingly, elevated markers of inflammation.

***We hypothesize that the same disease processes—in particular, persistent inflammation—that contribute to progressive LV dysfunction in mice with ICM and in patients with chronic HF, whether of ischemic or non-ischemic etiology, also contribute to progressive RV dysfunction found in many LVAD patients.***

Therefore...

- ***We further hypothesize that intravenous delivery of MSCs to patients with LVADs and RV failure will improve both LV and RV function, and therefore patient outcomes.***
- ***In addition, by reducing the excessive systemic inflammatory responses that exist in HF, the MSC-induced decrease in inflammation may improve multiple non-cardiac mechanisms that contribute to poor outcomes.***

### **3 STUDY OBJECTIVES**

#### **3.1 Primary**

To assess the safety of human allogeneic MSCs derived from bone marrow and administered intravenously—3 times at monthly intervals—to subjects with advanced HF of ischemic etiology (ischemic heart failure; IHF) or non-ischemic etiology (NICM) who underwent implantation of LVAD.

#### **3.2 Secondary**

To assess the efficacy of human allogeneic MSCs administered intravenously—3 times at monthly

intervals—to subjects with advanced HF who underwent implantation of LVAD : Specifically, effect on 1) right (RV) and left ventricular (LV) structure and function, 2) inflammatory and cardiac biomarkers, and 3) clinical status.

[figure not shown]
## 4 STUDY DESIGN

### 4.1 Description of the Study

This is a Phase IIa, double blind, placebo-controlled, multi-center, randomized study in subjects with advanced HF who are supported by LVADs.

The study will enroll 30 subjects and will consist of 2 cohorts. Enrolled subjects will be stratified by LVAD device type (HeartWare HVAD, HeartMate II or HeartMate III) and randomized at 1:1 into an experimental group (n=15) or a placebo group (n=15), respectively. Subjects in the experimental group will receive 1.5 million cells per kg, and subjects in the placebo group will receive 1.5 mL/kg Lactated Ringer's Solution at baseline, 1 month and 2 months.

All study participants will receive the MSCs or placebo within  $\pm 7$  days of the specified timing.

**Figure 4.1 Study Design**

Safety of study participants will be evaluated after each visit, as detailed in Appendix A. Physical examination and concomitant medications will be recorded at each infusion visit as well 90, 180, and 360 days. Complete examinations will be used to assess disability and functional status at baseline (prior to treatment) and at the visits scheduled at 1, 2, and 3 months after the initial administration. A baseline 2D and 3D and Doppler STEMVAD V1.5\_20200323

transthoracic echocardiography with speckle-tracking and gated blood pool SPECT ventriculography for assessment of right and left ventricular systolic function and volumes will be performed at baseline and at specific time points during follow-up. All echocardiograms will be assessed in a blinded core lab. All SPECT ventriculograms will be assessed by a blinded observer.

Subjects will continue all of their regular medications unless contraindicated. Subjects may be administered beta-blockers, ACE inhibitors, angiotensin receptor blockers or angiotensin receptor neprilysin inhibitor, mineralocorticoid receptor antagonists, isosorbide, hydralazine, mineralocorticoid receptor antagonists, statins, or other medications, as tolerated. Goal mean arterial blood pressure will be <85 mmHg. LVAD pump speed will not be adjusted unless the rationale for speed change is discussed with and approved by the principal investigator with the exception of an emergency situation.

## **SUBJECT PARTICIPATION**

Eligible participants must have advanced HF of ischemic etiology, defined as 1) a prior history of myocardial infarction and/or 2) angiographically (invasive or cardiac CT angiography) documented significant CAD (defined as a prior history of coronary revascularization (CABG or PCI) and/or obstructive CAD ( $\geq 75\%$  stenosis of the left main or proximal LAD or  $\geq 75\%$  stenosis of two or more major epicardial coronary arteries)) or non-ischemic cardiomyopathy etiology.

Enrollment window will open after discharge from index implant hospitalization and once the patient has been deemed stable with their LVAD implantation.

The screening evaluation will include obtaining written informed consent, collection of a complete medical history, including current and past medications, physical examination and laboratory tests. LVAD implantation is required for inclusion in the study.

A comprehensive 2D and 3D and 3D and Doppler transthoracic echocardiography with speckle tracking and gated blood pool SPECT ventriculography for assessment of right and left ventricular systolic function and volumes will be performed at baseline and at the specific time points during follow-up.

Eligible subjects will receive repeated infusions of either MSCs or placebo based on randomization at time 0 and at day 30 ( $\pm 7$  days) and day 60 ( $\pm 7$  days).

Follow-up visits will occur at days 7 ( $\pm 2$  days), 30 ( $\pm 7$  days), 37 ( $\pm 2$  days), 60 ( $\pm 7$  days), 67 ( $\pm 2$  days), 90 ( $\pm 7$  days), 180 ( $\pm 7$  days), and 360 ( $\pm 7$  days). Information on AEs, concomitant medications, vital signs, clinical laboratory tests and physical examination will be collected according to the schedule of assessments (Appendix A). All guideline-based medical care will continue as prescribed by the subject's personal physician(s). Use of other investigational agents or treatments is not allowed during this study.

### **Administration of Human Allogeneic MSCs**

The study will enroll a minimum of 30 subjects and will consist of 2 cohorts. Enrolled subjects will be randomized at 1:1 into an experimental group (n=15) or a placebo group (n=15). Subjects in the experimental group will receive 1.5 million cells per kg, and subjects in the placebo group will receive 1 mL/kg LRS at days 0, 30 and 60.

After the subject is randomized into one of the two cohorts, the final formulation of MSC or placebo will be prepared. Within 8 hours of infusion, the appropriate number of cells will be thawed at the study site pharmacy and re-suspended in LRS at a concentration of  $1 \times 10^6$  cells/mL. Subjects in placebo group will receive LRS at a volume of 1.5 mL/kg. The study solution (MSCs or placebo) will be labeled to ensure investigator blinding. The solution will be labeled to indicate that it is an investigational agent and will contain subject's identifying information, date, and time of formulation.

An intravenous line will be placed into a peripheral vein, and 0.9% sodium chloride solution will be run to keep the vein open. The study product will be drawn using an 18-gauge needle into a 60 mL syringe with an eccentric tip. The needle will be removed, and infusion tubing will be attached to the syringe. The syringe with infusion tubing will be placed in a metered dose syringe pump positioned horizontally with the syringe rotated such that the syringe tip is at the lowest position. The product will be infused intravenously into the subject's arm at a constant rate of approximately 2 mL/min. The applicable volume for the target dose will be delivered within  $\pm 2$  mL. Depending on subject's weight, up to three 60 ml syringes of product may be infused. After the entire product volume is delivered, 25 mL of LRS (without cells) will be infused at 2 ml/min to deliver cells from the infusion line for more accurate dosing. Subjects in the placebo group will receive intravenous LRS. Their syringes will be labeled as above to preserve blinding and followed by 25 ml of LRS infusion as above.

If the subject has an adverse reaction during the infusion, the infusion may be interrupted or slowed according to the severity of the reaction.

The following symptoms, if noted, during infusion may lead to slowing or cessation of the infusion session:

- Temperature  $\geq 39^{\circ}\text{C}$ .
- Unexplainable shaking chills.
- Angioedema.
- Respiratory distress.
- Wheezing/bronchospasms.
- Hypotension (Drop in MAP by  $\geq 20$  mmHg to an absolute MAP $<60$  mmHg).
- Hypoxemia (persistently reduced SpO2 of  $<88\%$ ).
- Any symptoms or signs, which in the investigator's opinion indicate clinical instability or a significant infusion reaction.

In the event the infusion session is prematurely stopped the investigator may opt to resume if the symptoms subside, however this will be at the discretion of the investigator. Adverse reaction duration the infusion, slowing or cessation of the infusion and any resuming of the infusion will be recorded on the case report form. If a session is prematurely stopped for adverse reaction, the patient will continue with the next interval follow up per the schedule of events.

All appropriate treatment will be given to reduce any discomfort and ensure the subject's safety. The infusion may be restarted, if interrupted, if the subject is not considered to be at risk by the Investigator and the subject consents.

All subjects will receive the follow-up tests and evaluations as detailed in Appendix A.

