## **5.2 Method of Treatment Assignment and Blinding**

This study is a Phase IIa, double-blind, placebo-controlled, multi-site (up to 2), randomized trial comprised of 30 subjects with an experimental group (stem cell infusion; n=15) and a placebo group (n=15; LRS at a volume of 1.5 mL/kg). Each group will receive 3 repeated doses of the assigned treatment (no cross-over) at times 0, 30 and 60 days. The infusion bags of stem cells or placebo will be identical.

In the event that a patient is unable to receive an infusion on or within the window of 30 or 60 days, the earliest infusion will be scheduled once it has been deemed safe for infusion. The primary endpoint measurement at day 90 (or within window) will remain irrespective to the number of infusions completed. More specifically, if infusion #2 (day 60) is missed then it will be scheduled as soon as the patient is deemed stable. The infusion #3 will occur 30 days from infusion # 2 but before day 90 (plus window) primary endpoint imaging evaluation. In the event that infusion # 3 would fall after the upper bound of the 90 day primary endpoint window then this infusion will be skipped.

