## **6.2 IV Administration of MSCs or Placebo**

An intravenous line will be placed into an appropriate peripheral vein with 0.9% sodium chloride solution running to keep the vein open. The study solution described above will be taken up in an 18 gauge needle into a 60 mL syringe with an eccentric (offset) tip. The needle will be removed and infusion tubing will be attached to the syringe. The syringe with infusion tubing will be placed in a metered dose syringe pump positioned horizontally with the syringe rotated such that the syringe tip is at the lowest position. The product will be infused intravenously into the subject's arm at a constant rate of approximately 2 mL/min. The applicable volume for the target dose will be delivered within 2 mL. Depending on subject's weight, up to three 60 mL syringes of product may be infused. After the entire product volume is delivered, 25 mL of LRS (without cells) will be infused at 2 mL/min to deliver cells from the infusion line for more accurate dosing. Subjects in the placebo group will receive intravenous LRS. Their syringes will be labeled as above to preserve blinding and followed by 25 mL of LRS infusion as above.

If the subject has an adverse reaction during the infusion, the infusion may be interrupted or slowed according to the severity of the reaction. All appropriate treatment will be given to reduce any discomfort and ensure the subject's safety. The infusion may be restarted, if interrupted, if the subject is not considered to be at risk by the Investigator and the subject consents.

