#### **During infusion:**

- IV infusion of the study product or placebo
- Monitoring for any signs of adverse reaction, record AE/s and concomitant medications
- Record vital signs and LVAD parameters every 2 hours, and as clinically indicated
- Continuous ECG monitoring during infusion of study product
- Pulse oximetry continuously during and for 2 hours post infusion

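### Minor: placebo volume is given once as 1 mL/kg against six statements of 1.5 mL/kg; separately, no timed temperature or MAP reading is assured while product is running

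*Combined protocol and SAP*

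**What the plan says.** **Placebo volume.** The subsection Administration of Human Allogeneic MSCs states in its first paragraph that "subjects in the placebo group will receive 1 mL/kg LRS at days 0, 30 and 60". Its second paragraph, which describes preparation, states "Subjects in placebo group will receive LRS at a volume of 1.5 mL/kg". Section 4.1 says "and subjects in the placebo group will receive 1.5 mL/kg", Section 5.1 gives the same figure, Section 5.2 describes the placebo as "LRS at a volume of 1.5 mL/kg", and Section 6.1 gives 1.5 mL/kg twice. The active dose is 1.5 million cells/kg, suspended at 1 million cells/mL.

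**Signs for slowing or stopping.** The same subsection says: "The following symptoms, if noted, during infusion may lead to slowing or cessation of the infusion session". The list opens with a temperature of at least 39 °C. It includes an entry that begins "Hypotension (Drop in MAP by" and continues with a fall of at least 20 mmHg to an absolute MAP below 60 mmHg.

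**Infusion and monitoring.** Product runs at about 2 mL/min, followed by a 25 mL flush at 2 mL/min. Section 6.2 allows that "up to three 60 mL syringes of product may be infused". Under During infusion, Section 7.2.2 instructs: "Record vital signs and LVAD parameters every 2 hours, and as clinically indicated". It also requires monitoring for adverse reactions, continuous ECG and continuous pulse oximetry. Vital signs are also taken before infusion, at no specified time, and two-hourly afterwards. The Appendix A footnote times them only for the period after infusion.

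**The concern.** **Placebo volume.** The blind relies on look-alike product and matching labels. If one arm received a smaller volume over a shorter time, staff or subjects could notice. The odd figure stands in current text, in the subsection that describes administration.

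**In-infusion readings.** Two of the numeric slow/stop signs can be detected reliably only by measuring, and neither ECG nor oximetry measures temperature or MAP. If the timed interval is longer than the infusion, the schedule does not ensure that either is measured while product is running. Symptoms can prompt an unscheduled check, but a fever or MAP fall without symptoms could pass unrecorded until afterwards. This bears on the plan's own aims: Background section 8 promises close observation for acute immune responses during infusion, and Section 4.2 lists temperature and mean arterial pressure under the primary safety endpoint.

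**Working it through.** **Inputs from the documents.** Dose 1.5 million cells/kg; concentration 1 million cells/mL; rate about 2 mL/min; flush 25 mL; at most three 60 mL syringes; vital-sign interval 120 min. **Assumed:** body weights, because the documents give none.

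**1. Which placebo volume is right?** Active volume = 1.5 million / 1 million = 1.5 mL/kg. This reproduces the six concordant statements (Section 4.1 opening, second paragraph of the administration subsection, 5.1, 5.2, and 6.1 twice) and not the single 1 mL/kg. Relative size of the outlier: 1 / 1.5 = 0.667, one third less.

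If a site used the outlier (product only, time = volume / 2):

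| Weight (assumed) | Placebo at 1 mL/kg | Active at 1.5 mL/kg |
|---|---|---|
| 60 kg | 60 mL, 30 min | 90 mL, 45 min |
| 80 kg | 80 mL, 40 min | 120 mL, 60 min |
| 90 kg | 90 mL, 45 min | 135 mL, 67.5 min |

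**2. How long does an infusion last?** Time = (1.5 × weight + 25) / 2. The syringe limit is 3 × 60 = 180 mL, which corresponds to 180 / 1.5 = 120 kg.

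| Weight (assumed) | Product + flush | Time | Short of 120 min by |
|---|---|---|---|
| 60 kg | 90 + 25 = 115 mL | 57.5 min | 62.5 min |
| 80 kg | 120 + 25 = 145 mL | 72.5 min | 47.5 min |
| 120 kg | 180 + 25 = 205 mL | 102.5 min | 17.5 min |

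So if the clock starts with the infusion and the infusion is not interrupted, the first two-hourly reading falls after the end of the flush at every weight within the syringe limit.

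**3. What would change that?**
- *A slower rate.* Mean rate at which infusion plus flush reaches 120 min: 115/120 = 0.96 mL/min at 60 kg (52% below 2), 145/120 = 1.21 at 80 kg (40% below), 205/120 = 1.71 at 120 kg (15% below).
- *An earlier clock.* If the two hours ran from the pre-infusion vital signs, a timed reading would fall within infusion plus flush when that set was taken more than 17.5 min before the start at 120 kg, or more than 47.5 min at 80 kg.

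**4. How often might it matter?** Background section 8 cites one reacting patient among 75 children with graft-versus-host disease: 1/75 = 1.3% (exact 95% CI 0.03% to 7.2%). That patient had two reactions in more than 500 infusions, so at most 2/500 = 0.4% per infusion. Over 15 × 3 = 45 active infusions, 0.004 × 45 = 0.18 expected reactions, if that rate carried over. This counts all such reactions, not those that the schedule would miss.

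**The case against.** **On the volume.** The 1 mL/kg stands in an enrollment summary sentence. Both preparation instructions, in the next paragraph and in Section 6.1, say 1.5 mL/kg, so a pharmacy would probably prepare the right volume. That stands. A reader might infer that the blind is compromised; the documents do not support that. The table above is conditional on a site following the outlier.

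**On the readings.**
- *The clock.* A reader might infer flatly that no timed reading can fall within an infusion. The documents do not go that far. Starting the clock with the infusion is the natural reading of an instruction headed During infusion, but it is not stated. The pre-infusion set has no specified time. It is listed with examination, blood draws and IV placement, and on days 30 and 60 with a walk test and echocardiography, so a long gap before the start is plausible. This stands, and limits the conclusion to readings not being assured.
- *The status of the list.* A reader might also infer that a stopping rule cannot operate, or that two statements conflict. The list is discretionary: signs may lead to slowing or stopping if noted. Nothing in Section 7.2.2 contradicts it. This is a monitoring gap, not an inconsistency.
- *Existing cover.* Unscheduled checks as indicated, adverse-reaction monitoring, continuous ECG and oximetry address symptomatic reactions. The one cited reaction involved breathing and oxygen saturation as well as temperature, came after the third and fourth infusions, and resolved. This stands too; what remains is a fever or MAP fall without symptoms, and the documents report no such event during infusion.
- *Mixed safety evidence.* Background section 7 reports transient fever as the one significant association, without onset time. It also reports no detected acute infusional toxicity, and no clinically significant adverse effects with the same product in the 23-patient NICM study. Background section 8 reports no infusional toxicities in a 62-patient randomized COPD trial.

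**Conclusion.** Both parts are minor.

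The 1 mL/kg is wrong as written. Six statements and the active dose give 1.5 mL/kg. This rests on counting and one division, and needs no assumption. The practical risk is small.

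The monitoring part is a worthwhile, inexpensive improvement. It assumes that the two-hour clock starts with the infusion, a rate near 2 mL/min, no interruption, and the three-syringe limit. On those terms infusion plus flush lasts at most 102.5 min against a 120-min interval, so the schedule does not assure a temperature or MAP reading after the start. An earlier clock or a slower infusion could bring one inside. The expected yield is low; the case rests on the small cost.

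**What to change.** 1. In the first paragraph of Administration of Human Allogeneic MSCs, change the placebo volume from 1 to 1.5 mL/kg. Cost: one figure.
2. In Section 7.2.2, During infusion, schedule temperature and MAP at a set interval shorter than the infusion and at the end of the flush. Keep the two-hourly readings for afterwards. Add the same in-infusion readings to the Appendix A footnote.

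Every 15 minutes would serve; that interval is an example and does not come from the documents. It gives 57.5/15 → 3, 72.5/15 → 4 and 102.5/15 → 6 readings at the assumed 60, 80 and 120 kg, plus one at the end of the flush: 4, 5 and 7 per infusion. Over three infusions that is 12 to 21 per subject, and over 30 subjects 360 to 630 in all. The readings are non-invasive, and monitoring is already required during the infusion. The text change is one line in each place.
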